14.5.2	Item 2 was clarified regarding termination requirements for persistent symptomatic hypotension, either not responding to bed rest or fluids.
15	Table 1 was modified to: 
 
• Add SOWS-Gossop at baseline.
 
• Add COWS at screening, baseline, and each day during treatment (Days 1-7 and Days 8-14).
 
• Add OOWS-Handelsman at screening.
 
• Replace the SCID with the M.I.N.I.
 
• To allow subjects to record the 3.5-hour post-dose vital signs measurements using a portable digital blood pressure machine if they are being treated on an outpatient basis and cannot stay in the clinic for this required post-dose measurement (see footnote j).
 

15.1	Screening assessments were clarified to include alcohol history. Text was revised to use the M.I.N.I. rather than SCID.
15.2	SOWS-Gossop was added as a required baseline assessment so it can be used as a covariate in the analysis.
15.4.1	First paragraph was clarified to provide a window ( $\pm 10$ minutes) for the 3.5-hour post first daily dose recording of the SOWS-Gossop. Also, text was clarified to indicate that for each daily evaluation, subjects should consider their symptoms over the last 24-hour period.
15.4.8; Appendix 6	Text was clarified regarding what should be recorded as withdrawal-related adverse events.

Location	Modification/Rationale
15.5.2	Second paragraph was clarified to provide a window ( $\pm$ 15 minutes) for the required 3.5-hour post-dose measurement of vital signs. Third paragraph, which pertains to the open-label part of the study (Days 8-14), was clarified to provide a window ( $\pm$ 30 minutes) for the required 3.5-hour post-dose measurement of vital signs. Also, a provision was added to allow subjects to record the 3.5-hour post-dose measurements using a portable digital blood pressure machine if they are being treated on an outpatient basis and cannot stay in the clinic for this required post-dose measurement.
15.5.3	Text was clarified to provide a window ( $\pm$ 15 minutes) for the required ECG recordings.
15.5.3	Text was clarified that an on-site qualified physician (rather than a cardiologist) will evaluate ECG tracings if there is significant abnormality.
16.2	Title of subsection and text was clarified to remove reference to FDA Form 3454 because the Sponsor (US WorldMeds) will provide a Financial Disclosure form (internal template) to each site for signature.

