2. SAMPLE SIZE

Treatment effect and subject variability with respect to SOWS-Gossop scores were estimated from the prior Phase 3 study (USWM-LX1-3002), using the random coefficients model planned for the present study and estimating the treatment effect of 3.2 mg lofexidine versus placebo with respect to area under the curve (AUC) based on the SOWS-Gossop scores from Days 1 through 7 (AUC(1-7)). It was assumed that the treatment effect of the 2.4 mg lofexidine dose will be three-fourths the treatment effect of the 3.2 mg dose. The table below shows the power to find a significant treatment effect for the comparisons of the two lofexidine treatments versus placebo, assuming a sample size allocation ratio of 3:3:2 (3.2 mg lofexidine : 2.4 mg lofexidine : placebo) and accounting for the sequential testing approach described in Section 6.1. The power to find a statistically significant effect of the 3.2 mg lofexidine dose with respect to AUC (1-7) is in excess of 90% with the planned total sample size of 600.

	Power (%) with Respect to AUC (1-7)		
Total Sample Size	3.2 mg Lofexidine versus Placebo	2.4 mg Lofexidine versus Placebo	
600	94.6	72.6	
550	92.6	67.6	
500	90.1	62.2	
450	86.8	55.7	

Effective: 14-Feb-13

Page 4 of 26

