6.2 Derived Data

• Definition of baseline

For all variables, baseline is defined as the last non-missing value prior to the receiving the first dose of study medication.

All tabulations involving change from baseline data will only include subjects with cohort data i.e. with data at baseline and at follow-up. Change from baseline will be calculated as follow-up values minus baseline value.

• Incomplete dates

All incomplete dates will be included in the clinical database as they were entered in the eCRF. Thereafter for calculation purposes, the incomplete dates will be completed using pre-defined rules. If a day or month is not recorded it will be replaced by the first day of the month or January respectively, provided this does not contradict any other dates recorded. For missing adverse events and medications dates/times during the trial, the worst-case date will be used (e.g. the end of the month for a stop date and 23:59 for the stop time, the date/time of initial dose for start of AE i.e. all events with missing start dates will be assumed to be treatment emergent).

• Ambiguous values

In the case where a variable is recorded as ">x", " \geq x", "<x" or " \leq x", then for analysis purposes a value of x will be taken. Where a range of values is quoted the midpoint of the range will be taken.

Effective: 14-Feb-13

Page 6 of 26

• Questionnaire Data

In the event that component items used to calculate total scores for questionnaire data e.g. SOWS Gossop score are missing then the total scores will also be set to missing.

• Site pooling for statistical analyses

For the purposes of statistical analyses models where site is included within the model as a fixed effect, sites randomizing < 6 subjects will be pooled from smallest to largest until the pooled site subsequently created has at least 6 subjects. In the event that the pooling of sites with less than 6 subjects does not result in a site with > 6 subjects, then that pooled site with < 6 subjects will also be pooled with the next largest site with > 6 subjects. To break ties if more than one site has the same number of subjects, the site identifier will be used as a secondary sort key.

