6.12 Multiplicity

For the primary and secondary endpoints, the treatment comparisons subject to control of the false positive rate will be 3.2 mg lofexidine vs. placebo and 2.4 mg lofexidine vs. placebo. Comparisons of 3.2 mg vs. 2.4 mg will be descriptive. The familywise error rate (FWE) for the collection of primary and secondary endpoint comparisons will be controlled at the 0.05 level, two-sided, by a sequential testing strategy in which hypotheses are tested in the following order, each at the 0.05 level, using a two-sided test.

- 1. Primary: AUC(1-7), 3.2 mg lofexidine versus placebo;
- 2. Primary: AUC(1-7), 2.4 mg lofexidine versus placebo;
- 3. Secondary: Completion rate, 3.2 mg lofexidine versus placebo; and
- 4. Secondary: Completion rate, 2.4 mg lofexidine versus placebo.

The tertiary/exploratory endpoints will be tested without multiplicity adjustment.

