6.14 Change to Planned Protocol Analysis

The following changes have been made to the planned protocol analyses sections:

Section 17.2.7 Control of the False Positive Rate and Statistical Testing Strategy

Change: All statistical tests will be two-sided at the 0.05 significance level. This is a change from the protocol, where it was specified that statistical tests would be one-sided at the 0.025 significance level.

Reason: Two-sided statistical tests at the 0.05 significance level is statistical convention for hypothesis testing.

Section 17.2.8.1 SOWS-Gossop AUC (1-7)

Change: A number of sensitivity analyses have been added and are detailed in section 16.9.2 of the statistical analysis plan.

Reason: To provide additional sensitivity analyses of log_e (SOWS-Gossop score +1) from day 1 to day 7 under differing mechanisms for missing data, including Missing at Random (MAR) and Missing Not at Random (MNAR)

Section 17.2.8.2 Completion Status

Change: A logistic regression model including fixed effects for treatment group, gender and site will be used instead of a Cochran-Mantel Haenszel test to test for a difference in completion status between the 2 Lofexidine groups and placebo.

Reason: To additionally adjust for site in the analysis and to provide an interpretation of the effect of treatment using odds ratios.

Sections: 17.2.8.3 SOWS-Gossop on Days 1, 2, 3, 5, 6 and 7 and 17.2.8.4 OOWS-Handelsman, MCGI (Subject and Rater), VAS-E, and COWS

Change: A MMRM model will be used to test for a difference in the log_e (SOWS-Gossop score +1) at each of days 1 through 7 between the 2 Lofexidine groups and placebo. This replaces planned pattern-mixture approach used in the principal analysis.

Reason: MMRM model is a standard approach for the analysis of treatment differences at different time points when there are repeated measures.

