2. CHANGES TO EXISTING ANALYSIS PLAN

Change 1

Section 6.1 General

Add following sentence

For all statistical models analyzed via log-transformed data the back-transformed LS means will be presented in the output.

Change 2

Section 6.2 Derived Data

Site Pooling for Statistical Analysis

The following text was removed:

For the purposes of statistical analyses models where site is included within the model as a fixed effect, sites randomizing < 6 subjects will be pooled from smallest to largest until the pooled site subsequently created has at least 6 subjects. In the event that the pooling of sites with less than 6 subjects does not result in a site with > 6 subjects, then that pooled site with < 6 subjects will also be pooled with the next largest site with > 6 subjects. To break ties if more than one site has the same number of subjects, the site identifier will be used as a secondary sort key.

Justification

The primary analysis no longer includes site in the model; therefore site has been removed as a variable from all subsequent statistical models.

Effective: 24-Dec-2014

Page 3 of 29

Change 3

Section 6.3 Analysis Populations

An additional population has been added

The **per-protocol population.** This analysis set will be a subset of the mITT population and will consist of all subjects who satisfy all of the inclusion/exclusion criteria and who correctly receive the treatment to which they are randomized and do not have a major protocol deviation within the double-blind phase. The selection of subjects for the per-protocol population will be made prior to database lock. Major protocol deviation will be broadly classified into five main categories based on ICH Harmonised Tripartite Guideline Structure and Content of Clinical Study Reports E3:

- 1. those patients who enter the study despite not satisfying entry criteria
- 2. those patients who developed non-safety related withdrawal criteria during the study and were not withdrawn
- 3. those patients who received the wrong treatment
- 4. those patients who received an excluded concomitant treatment, defined as any drug that is not included in the approved list of medications (as outlined in Appendix 16.2.2) or any antibiotic
- 5. lack of major compliance with the protocol.

The only variable to be assessed using the per-protocol analysis set will be the primary efficacy endpoint.

Justification

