It will be assumed that subjects randomized to lofexidine who withdraw from the study will have a time trajectory comparable to placebo post withdrawal. The pattern-mixture model will be implemented using multiple imputations (Ratitch⁶, 2011). The imputation of missing values and the analysis will be performed multiple times (20 imputed datasets) with the initial seed value set at '123', and the inference of this sensitivity analysis will be based on the combined estimates using the standard multiple imputation technique. This method is detailed in the section entitled "Pattern-Mixture Model with Control-Based Pattern Imputation" (Ratitch⁷, 2013). Briefly, the initial step is to impute the relatively rare, non-monotone missing data via the MCMC Option of SAS® PROC MI. This step uses iterative methods, with which non-convergence is a possibility; should an MCMC imputations that converge will be used in the analysis. This imputation model will be implemented for each combination of gender and treatment. (It should be noted that by performing the imputation for each such combination, the imputation modelling will be richer than the model used to inferentially analyse the data. It is acceptable, even preferable, for the imputation model to be richer than for the analysis model (see Little and Rubin, 2002).

The next step applies to the monotone missing data. The values for each pattern will be imputed using the chained equation method by SAS® PROC MI option MONOTONE REG. This MNAR imputation employs only the appropriate data for each pattern. That is, the missing data for lofexidine treatment arm at time t will be imputed using only the data on placebo subjects up to time t and the data for lofexidine subjects who have data up to time t-1 but are missing data at time t. The model for imputing missing data at time t will include fixed effect terms for study day from the baseline visit through to the t-1 visit and sex. Note that a term for treatment group is not included in this imputed data sets will be analyzed using the MMRM model described below and then summarized using PROC MIANALYZE. The model will include fixed effects for treatment group, baseline log_e (SOWS-Gossop score +1), sex, study day (days 1-7), and

Effective: 24-Dec-2014

Page 7 of 29

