Additionally, further efficacy analysis will be conducted using the area under the curve (AUC) from Days 1 through 7 of the SOWS-Gossop scores as the endpoint. The AUC will be calculated on the original scale of measurement based on the back-transformed log scale estimates from the pattern mixture analysis. The LS means of the daily SOWS-Gossop scores (Days 1 through 7) will be exponentiated to get the geometric mean SOWS-Gossop score for each day. These back-transformed scores will then be used to calculate the AUC using the trapezoidal rule. AUC summary statistics will be reported, no formal statistical analysis will be performed.

Justification

The additional analysis was added to incorporate comments from the US Food and Drug Administration (FDA) regarding an additional proposed efficacy analysis. Since statistical inference on the AUCs, such as confidence intervals, would be difficult and the results at best

Effective: 22-Jan-2015

Page 4 of 11

approximate, due to the fact that a propagation of errors approach would be needed to accommodate the exponentiation of results from the log scale of measurement back to the original scale; we have elected to present the estimated AUC values as descriptive statistics.

Change 4

Section 6.10 Secondary Endpoint

The following text was amended:

The secondary efficacy endpoint is the completion status (i.e., whether a subject receives at least one dose of study medication on Day 7 and completes the 3.5-hour post-dose SOWS-Gossop assessment on Day 7). The proportion of subjects in each treatment arm who receive at least one dose of study medication on Day 7 and complete the 3.5-hour post-dose SOWS-Gossop assessment on Day 7 will be analyzed using a logistic regression model including fixed effects for treatment group and gender using the mITT population. One test will compare the 3.2 mg lofexidine group to placebo; a second will compare the 2.4 mg Lofexidine group to placebo. A sensitivity analysis will be performed on this endpoint using the ITT population.

Justification

Gender was inadvertently removed as a variable from the logistic regression model.

Change 5

Section 6.2 Assessments Recorded at Discontinuation Visit

Add the following text related to handling assessments recorded on discontinuation visit:

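### The confirmatory completion-status model adjusts for gender only; adding baseline SOWS-Gossop, already collected for covariate use, is a cheap efficiency gain

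*SAP*

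**What the plan says.** The current text of SAP Section 6.10 (Addendum 2, Change 4) has completion "analyzed using a logistic regression model including fixed effects for treatment group and gender using the mITT population", with an ITT sensitivity analysis. Section 6.12 places completion third and fourth in the controlled sequence, beginning with "Secondary: Completion rate, 3.2 mg lofexidine versus placebo".

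The baseline score is available. Protocol Section 15.4.1 schedules it before randomization. The Amendment 1 log gives the reason for Section 15.2: "SOWS-Gossop was added as a required baseline assessment so it can be used as a covariate in the analysis". The current primary model (Addendum 1, Change 7) uses it: "The model will include fixed effects for treatment group, baseline log_e (SOWS-Gossop score +1), sex, study day (days 1-7), and" a treatment-by-day interaction.

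The completion analysis has changed three times:
- Protocol 17.2.8.2: Cochran-Mantel-Haenszel (CMH) test stratified by gender.
- SAP 6.10: logistic regression with treatment, gender and site. Section 6.14 gives the reason: "To additionally adjust for site in the analysis and to provide an interpretation of the effect of treatment using odds ratios".
- Addendum 1: site removed. Change 2 explains: "The primary analysis no longer includes site in the model; therefore site has been removed as a variable from all subsequent statistical models".
- Addendum 2: edited only to put right an accidental loss of gender.

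**The concern.** One of the two stated reasons for leaving the CMH test was to adjust for a further variable. With site gone, the logistic model adjusts for the same single factor as the test it replaced. Site was removed because the primary model no longer carried it. The same reasoning was not applied to baseline SOWS-Gossop, which the primary model does carry.

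A link with completion is plausible from the documents. SAP 6.6 lists intolerable withdrawal symptoms first among the reasons for double-blind withdrawal, and SAP 6.9.3 treats baseline SOWS-Gossop as a key baseline characteristic. If the score predicts completion, leaving it out gives up power on two tests that support formal claims. No power is stated for completion; SAP Section 2 covers only the former AUC endpoint.

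**Working it through.** **1. The plan's own figure.** SAP Section 2 gives 94.6% (3.2 mg) and 72.6% (2.4 mg) for AUC(1-7) at N = 600, "accounting for the sequential testing approach described in Section 6.1". No effect size or SD is given, so 94.6% serves as the anchor. The drift is 1.96 + 1.607 = 3.567. At three-fourths of that effect, 0.75 x 3.567 - 1.96 = 0.715, a marginal power of 76.3%. The product 0.946 x 0.763 = 72.2% is close to the stated 72.6%. So 72.6% can be read as the chance that both primary tests succeed, with the two tests treated as independent.

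**2. Gain from the covariate.** From the documents: 225 vs 150 subjects, two-sided 0.05, gender in the model. Assumed: the completion rates, the effect, and the odds ratio (OR) of completion per SD of baseline severity. Effects were set to give about 80% power with gender only. There were 10,000 simulated trials per setting, with a Wald test (z > 1.96) and marginal rates held fixed. Power (%) without vs with the covariate:

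| OR per SD | 30% vs 44% | 40% vs 54.8% | 50% vs 64.5% | Gain (points) |
|---|---|---|---|---|
| 1.0 | 79.3 / 79.3 | 80.0 / 79.9 | 79.8 / 79.9 | -0.1 to 0.1 |
| 0.8 | 78.6 / 78.8 | 80.7 / 81.4 | 79.0 / 79.3 | 0.2-0.7 |
| 0.7 | 78.3 / 79.2 | 80.1 / 81.3 | 80.0 / 80.9 | 1.0-1.2 |
| 0.6 | 78.6 / 81.0 | 80.9 / 83.0 | 80.2 / 82.1 | 1.9-2.4 |
| 0.5 | 79.3 / 82.7 | 80.7 / 84.3 | 79.7 / 83.4 | 3.3-3.8 |

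Gains were taken before rounding, so they can differ by 0.1 from the displayed figures. Their Monte Carlo SE is 0.09-0.27 points. A separate simulation of all three arms (4,000 trials per setting) gave about 3-4 points at OR 2.0 for non-completion, which is the same strength as 0.5 for completion, and 6-10 points at OR 3.0.

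**3. Mechanism.** At 40% and OR 0.5, the mean log-OR moves from 0.604 to 0.672 and its mean SE rises from 0.215 to 0.228. The ratio goes from 0.604/0.215 = 2.81 to 0.672/0.228 = 2.95. On the risk-difference scale, the empirical SD of the standardized estimate falls from 0.0515 to 0.0490, about 5%.

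**4. Type I error.** One-sided at 40% vs 40%: 2.35-2.56% without the covariate and 2.48-2.65% with it (nominal 2.5%).

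**5. Gating.** Completion is tested only after both primary tests succeed. With 0.726 and independence:
- OR 0.7: 1.0 x 0.726 = 0.7 to 1.2 x 0.726 = 0.9 points.
- OR 0.5: 3.3 x 0.726 = 2.4 to 3.8 x 0.726 = 2.8 points.

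**6. Missing baseline.** If a fraction f of subjects were dropped, power falls from 80% to Phi(2.80 x sqrt(1 - f) - 1.96). That gives 79.6%, 79.2% and 78.0% for f = 1%, 2% and 5%, losses of 0.4, 0.8 and 2.0 points. These rates are assumed. A weak gain could be cancelled.

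**The case against.** The strongest reply is that nothing is broken. The gender-adjusted test holds its type I error, and gender is the only randomization stratification factor (Protocol 14.3.2, SAP Section 3), so adjusting for it alone is a principled choice. The Amendment 1 log ties the analysis change for this covariate to Protocol 17.2.8.1, the primary analysis. No version of the plan promised it for completion. Removing site because the primary model lost it does not commit the plan to carrying every primary covariate into every model. All of this stands.

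Prognostic value is also less certain here than in the primary model, where the covariate and the outcome are the same scale. Subjects can fail to complete for cardiovascular criteria, missed doses, illicit drug use or non-compliance (Protocol 13.2.3 and 14.5.1). That stands too, and it is why the gain is given as a range starting at zero.

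The gating factor belongs to the superseded AUC endpoint and assumes independence. Positive correlation between completion and the symptom outcome would trim the gain: with correlations of 0.3-0.7, a gated gain of 0.82 points at OR 0.7 becomes 0.75-0.69. The order of magnitude does not change.

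Missing baselines should be rare, because Protocol 14.3.1 randomizes subjects who complete all baseline measures and Addendum 2 prorates missing items. That lowers the expected loss, but a one-line rule is still worth having. None of these points makes the change costly or the observation wrong.

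**Conclusion.** The point holds as a recommended improvement. The completion model leaves out, without explanation, a pre-randomization covariate that the trial already collects and uses in its primary model. The planned analysis is valid and breaks no commitment.

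The benefit is negligible if baseline severity is weakly prognostic, around one point at OR 0.7 per SD, and three to four points at OR 0.5, before the gating reduction. The completion rates, effect and prognostic strength are all assumptions, since the documents give none of them. The table's figures are for a single dose compared with placebo at about 80% power; no separate figure is claimed for 2.4 mg. Confidence is medium, because the size turns on an unknown prognostic strength.

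**What to change.** Before unblinding, amend SAP Section 6.10 as follows:
- Add baseline log_e(SOWS-Gossop+1) to the logistic model for both the mITT and ITT analyses, and keep gender.
- State a missing-baseline rule that drops no subject, for example substituting the overall baseline mean pooled across arms.
- Define baseline for ITT subjects who were never dosed as the last pre-randomization score. SAP 6.2 ties the definition to dosing: "baseline is defined as the last non-missing value prior to the receiving the first dose of study medication".
- Report a standardized marginal risk difference with its 95% CI beside the odds ratio, and name the CI method.

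If the sponsor prefers the current model, one sentence should record why. The covariate is optional in the exploratory retention, MCGI severity and VAS-E models, and no gain is claimed there.

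The cost is a short SAP paragraph, with no added visit or procedure. The odds ratio becomes conditional on baseline severity, which is why the marginal measure is needed.

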### 15.3.3 Study Discontinuation/End of Study

Any subject that discontinues from the study, regardless of the reason (see all scenarios listed in [Section 14.5.1](#)), will be requested to complete all Study Discontinuation/End of Study assessments and procedures as listed below after the last dose of study medication:

- Concomitant medication assessment.
- Completion of detoxification as assessed by the Site Investigator.
- Pill count to measure compliance with previous day’s doses if not already performed.
- Blood pressure and pulse at rest (sitting or recumbent, if required, for treatment of an AE) and standing; respiration, and temperature.
- AE assessment.
- 12-lead ECGs (in duplicate).
- Clinical laboratory tests.
- Complete physical examination (including body weight).
- Pregnancy test.
- Urine drug screen.
- C-SSRS (Since Last Visit version; [Appendix 10](#)).
- SOWS-Gossop.
- OOWS-Handelsman.
- MCGI (Subject and Rater).
- VAS-E.
- COWS.

A 30-day post discharge follow-up telephone contact will be made 30 days after the subject’s last dose for an adverse event evaluation and an evaluation of the subject’s current treatment status (e.g., relapse, current psychosocial treatment, successful entry into a methadone, buprenorphine, or naltrexone program).

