Operational Note: When a vital sign or QTcF reading meets any of the defined cut-off criteria for discontinuation, the values will be confirmed by repeating the measurement twice, approximately 10 to 15 minutes apart. If 2 of the 3 total readings confirm that the subject meets discontinuation criteria, the subject will be terminated from the study. If 2 of the 3 total readings are within acceptable limits (and they do not meet the other discontinuation criteria detailed in [Section 14.5.2](#)), the subject may continue in the study.

Additionally, when the subject is experiencing blood pressure- or pulse-related symptoms (e.g., lightheaded, dizziness, palpitations), these should be recorded in the subject's source document and eCRF as an AE or SAE (see [Sections 15.5.1](#), [16.7](#), and [16.8](#)) even if the vital signs values do not meet the predefined criteria shown above.

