6. ANALYSIS PLAN

6.1 General

The treatment groups will be labelled as 2.4 mg Lofexidine, 3.2 mg Lofexidine and Placebo within the statistical output. In addition the 2.4 mg Lofexidine and 3.2 mg Lofexidine doses are

Effective: 14-Feb-13

Page 5 of 26

combined to form a single Lofexidine treatment group for presentation of safety data. Subject data in Appendix 16.2 listings will be ordered by treatment group, site and subject.

All statistical tests for efficacy will be 2-sided at the α =0.05 significance level.

All comparisons between the treatments will be reported with 95% confidence intervals for the difference. P-values will be rounded to four decimal places.

Only scheduled post-baseline laboratory and vital signs values will be tabulated. Post-baseline repeat/unscheduled assessments will be disregarded, although they will be listed in the relevant appendices to the report; in particular all clinically significant values will be noted.

All calculations and figures will be produced using SAS Version 9.3³ or higher.

All summaries and analyses documented below will be presented in the final integrated statistical/clinical report and tables that will be based on the E3 guidelines published by ICH. However, it is noted here that no analysis plan prepared in advance of the data can be absolutely definitive and so the final report may contain additional tables or statistical tests if warranted by the data obtained. The justification for any such additional analyses will be fully documented in the final report.

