The following will be summarized and analyzed separately for the double blind and open label study phases:

- 1. To assess safety:
 - a. **Suicidality:** The number and percentage of subjects reporting any suicidal ideation or behavior throughout the assessment period.
 - b. **Suicidal behavior only:** The number and percentage of subjects reporting any type of suicidal behavior throughout assessment period.
 - c. **Suicidal ideation only:** The number and percentage of subjects reporting any type of suicidal ideation throughout assessment period.

In addition, taking into account baseline data regarding suicidal ideation to determine if suicidal ideation or behavior has worsened:

d. **Emergence of suicidal ideation:** The number and percentage of subjects reporting no suicidal ideation at baseline and any type of ideation during the assessment period.

Effective: 14-Feb-13

Page 21 of 26

- e. Emergence of serious suicidal ideation: The number and percentage of subjects reporting no suicidal ideation at baseline and had serious suicidal ideation (as defined above; score of 4 or 5 on suicidal ideation severity rating) during the assessment period.
- f. **Worsening of suicidal ideation:** The number and percentage of subjects whose most severe suicidal ideation rating is more severe than it was at baseline.
- g. **Emergence of suicidal behavior:** The number and percentage of subjects who had no suicidal behavior at baseline and any type of behavior during the assessment period.

For each of the above endpoints a-g, Fisher's Exact test will be used to test for a difference between the 2 Lofexidine treatment groups and placebo during the double blind phase only.

Physical Examination

The body systems within the physical examination data at screening, baseline (day 1), day 7 and end of the study will be summarized by treatment (Normal; Abnormal NCS, Abnormal CS). The changes from baseline to end of the study in bodyweight will also be tabulated.

Concomitant medications

Concomitant medication verbatim terms (as recorded on the CRFs) after the initial dose of study drug will be mapped to Anatomical Therapeutic Chemical (ATC) Level 2 and Drug Reference Names using the World Health Organization (WHO) dictionary (Version 3.13 Enhanced) and tabulated by treatment group and overall.

Psychosocial Therapy Sessions

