On days where a discontinuation visit is recorded on the same day as a scheduled visit, then the **scheduled visit** should be used be for analysis purposes and the discontinuation visit will be ignored. If a discontinuation visit is recorded on a study day where no scheduled visit is recorded, then it should be assigned to the **actual study day** the visit was recorded.

Justification

Effective: 22-Jan-2015

Page 5 of 11

To further clarify a set of rules for how to handle assessments recorded on the date of discontinuation instead of the scheduled study visit.

Change 6

Section 6.9.1 Principal Analysis

The following text in bold has been revised:

A pattern-mixture approach⁵ will be used in assessing SOWS-Gossop from Days 1 to 7 inclusive using the mITT population.

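### SAP Addendum 2 Change 5 sets aside a same-day discontinuation visit without limiting the rule to efficacy data, so exit C-SSRS and last-value safety results can be lost

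*SAP*

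**What the plan says.** **The rule.** Addendum 2 Change 5 is placed in SAP Section 6.2 (Derived Data). With a scheduled and a discontinuation visit on one day, the scheduled visit "should be used be for analysis purposes and the discontinuation visit will be ignored". The next sentence covers the other case: with nothing scheduled on record for that day, the exit visit is kept and dated to the day on which it took place. The stated justification is to clarify "how to handle assessments recorded on the date of discontinuation instead of the scheduled study visit". No variable or domain is named.

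**What is collected at exit.** Protocol 15.3.3 says that any subject who discontinues "will be requested to complete all Study Discontinuation/End of Study assessments and procedures as listed below after the last dose of study medication". The list includes the C-SSRS (Since Last Visit form), vital signs, laboratory tests and body weight, as well as the efficacy scales.

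**How the safety data are summarized.** SAP 6.13 defines C-SSRS endpoints a-g over a period and not by visit. Endpoint a, for example, is "The number and percentage of subjects reporting any suicidal ideation or behavior throughout the assessment period". Endpoint f uses the most severe ideation rating. In the double-blind phase all seven are compared with placebo by Fisher's exact test. Vital signs have a double-blind endpoint summary, laboratory values a summary of the last double-blind and last open-label assessment, and body weight a change from baseline to end of study.

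**A separate rule.** SAP 6.1 states: "Only scheduled post-baseline laboratory and vital signs values will be tabulated". Repeat and unscheduled values are left out of the tables but listed.

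**The concern.** One value per day, taken at a fixed time after the first dose, is what a repeated-measures model of the SOWS-Gossop needs. An any-time or worst-value safety endpoint needs the opposite: every value up to exit. Change 5 applies the first principle to all assessments.

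The values at risk are those recorded as the subject leaves. The Protocol hypothesizes that completion differs between lofexidine and placebo (Section 7), and its disposition strata anticipate exits for lack of efficacy and for drug intolerability (17.2.8.1). Any loss at exit could therefore differ by arm. That would affect the C-SSRS comparisons with placebo and the descriptive 2.4 mg versus 3.2 mg safety comparison named in the objectives.

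**Working it through.** The plan has no figure to reproduce. The check counts the schedule and then applies the rule to it.

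**Schedule, Days 1-7** (Protocol 15.3.1, 15.5.2, 15.5.6)
- Doses at 8 AM, 1 PM, 6 PM and 11 PM.
- Vital signs: 4 pre-dose + 3 post-dose = 7 sets a day, nominally 8:00, 11:30, 13:00, 16:30, 18:00, 21:30 and 23:00. This agrees with the Protocol's own count of seven.
- C-SSRS: 8:00 + 3.5 h = 11:30 AM, every day.
- The C-SSRS is also daily on Days 8-14, so it is planned on 14 of 14 treatment days.

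**Applying Change 5 to an exit on Days 1-7**

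| Exit data | Rule judged per assessment | Rule judged per visit |
|---|---|---|
| C-SSRS, exit after about 11:30 AM | set aside | set aside |
| C-SSRS, exit before about 11:30 AM | kept | unclear: do the pre-dose vital signs alone make a scheduled visit? |
| Vital signs, same day as a scheduled set | set aside | set aside |
| Laboratory tests and weight | normally kept | set aside |

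**C-SSRS.** The exit form asks about the time since the last assessment. Take a subject with no ideation at baseline and a negative C-SSRS at 11:30 AM on Day 3, who leaves at 8 PM. The exit form is the only one covering 11:30 AM to 8 PM, which is 8.5 hours. The 30-day telephone contact covers adverse events and treatment status, not the C-SSRS. If ideation is reported at exit, setting the form aside makes this subject a non-event in endpoints a, c, d and f. With a rating of 4 or 5 the subject is also missed in e.

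**Vital signs.** The SAP does not define the double-blind endpoint. If it means the last double-blind value, Change 5 replaces the exit set with an earlier set from the same day.

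**Laboratory values and weight.** Table 1 of the Protocol schedules weight only at screening and at discontinuation. For an early leaver with no laboratory test done on clinical grounds, the exit sample is the only post-baseline sample. A whole-visit reading would remove the data that these two summaries need.

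**How often.** A completer must have a recorded Day 7 post-dose SOWS-Gossop, so a completer whose discontinuation visit is dated Day 7 always meets the same-day condition. For other exits the answer depends on the hour. The documents give no exit times, so the share with a same-day scheduled C-SSRS already recorded could lie anywhere from 0% to 100%.

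**The case against.** The best defense is that Change 5 is a visit-mapping rule, as its justification suggests, and that the specific C-SSRS wording in SAP 6.13 prevails over a general rule. The weight and laboratory summaries support this, because a blanket reading would defeat them. It is a reasonable account of intent, but the text does not say it. Change 5 refers to analysis purposes without limit, and two programmers could produce different C-SSRS tables from it.

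The second defense is adverse event reporting, and it stands in part. Protocol 15.5.2 sends qualifying vital signs, and symptoms related to blood pressure or pulse, to the adverse event record. Section 16.7 does the same for C-SSRS findings judged clinically significant, with a score of 3 or more as the example. A rating of 4 at exit would therefore very likely appear among the adverse events. A rating below 3 might not, yet it counts in endpoints a, c and d. In either case the C-SSRS table itself is not restored.

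A reader might infer more than the documents support:
- **That every exit assessment is dropped.** The rule needs a scheduled visit recorded that day. Otherwise the exit visit is kept.
- **That SAP 6.1 also removes C-SSRS data.** It names only laboratory and vital-sign values. The discontinuation visit is a planned column of Table 1, so calling it unscheduled is an inference.
- **That the blood-pressure cut-off counts hide discontinuation readings.** These counts are by visit (Addendum 1, Change 15), so scheduled values are their natural input. When a reading meets a discontinuation limit, "the values will be confirmed by repeating the measurement twice, approximately 10 to 15 minutes apart", and leaving out those repeats does not hide a scheduled trigger. Entry requires systolic pressure of at least 95 and diastolic of at least 65 mmHg at screening. A systolic reading below 70 is more than 95 - 70 = 25 mmHg below screening, and a diastolic reading below 40 is more than 65 - 40 = 25 mmHg below. Both already meet the SAP cut-offs (at most 90 with a fall of at least 20; at most 50 with a fall of at least 15).

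**Conclusion.** The point holds for Change 5 alone. As written, it sets aside the exit C-SSRS of a subject who leaves on Days 1-7 after that day's scheduled C-SSRS, contrary to endpoints a-g. It also displaces the same-day exit vital signs from the double-blind endpoint summary. On a whole-visit reading it conflicts with the last-value laboratory and end-of-study weight summaries. These summaries may be understated, possibly differently by arm.

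The size is unknown. A reader might assume that 40-60% of the 600 subjects leave before Day 7 and arrive at 240-360 affected. The documents give no such rate, and the figure would count exits, not lost findings. A finding is lost only if the exit follows a recorded same-day assessment, the exit form is completed and positive, and no earlier assessment has already counted the subject. For the same reason the documents do not show that the Fisher tests are biased, or in which direction. The conclusion rests on a literal reading of Change 5 and on taking endpoint to mean last value. The efficacy analyses are not affected by this point.

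**What to change.** Limit Change 5 to the daily efficacy scales: SOWS-Gossop, OOWS-Handelsman, MCGI, VAS-E and COWS. Then add to SAP 6.13, for example:

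> C-SSRS endpoints a-g, and the last-value or endpoint summaries of vital signs, laboratory values and body weight, include values recorded at the discontinuation visit, whether or not a scheduled visit was recorded on the same day.

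By-visit vital-sign means and blood-pressure cut-off counts can continue to use scheduled values. Repeat and unscheduled readings need not be added to them.

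The cost is about two sentences of SAP text and minor programming. The Protocol already provides for collecting the data.
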